## 1.5 RESEARCH HYPOTHESIS

We hypothesize that use of a novel, simplified trial design which incorporates withdrawal of confounding background immune suppressants with a robust clinical efficacy endpoint, a greater number of patients with SLE who are randomized to abatacept will achieve the primary efficacy endpoint of BICLA than patients randomized to placebo.

## 1.6 STUDY RATIONALE

This double blind placebo controlled study will randomize lupus patients with active arthritis to abatacept or placebo for a six month trial to determine which group has a greater response rate as measured by the primary endpoint of BICLA (BILAG based Combined Lupus Assessment ) (BILAG=British Isles Lupus Assessment Group index). The dose of 125 mg administered subcutaneously weekly has been validated in an RA population and was chosen for this study in SLE on the basis of the assumption that it will be equal in efficacy to intravenous infusion without adversely affecting the safety profile. This current small study is not designed to test that assumption, but on the basis of RA data it seems reasonably likely that any efficacy signal from abatacept will be detectable through this route of administration in SLE. Subcutaneous dosing is a more practical clinical approach in the management of patients overall, is much easier for the patients, and will lessen the costs of an investigator initiated study while being unlikely to negatively affect either patient safety or the information that can be obtained.

The rationale for this study design, which is based on exploratory analysis of previous abatacept and other lupus studies, is to provide a more discriminatory protocol and a more robust endpoint than was available in prior trials for lupus. A further rationale is to provide proof of concept for the general feasibility of smaller pre-Phase III trials in SLE with greater potential effect size than has been possible in the past and ability to make confident go/no go decisions for Phase III development after less investment of time, patient risk, and expense than is usual in Classic Phase II designs.

Indeed this project is specifically powered (based on data about placebo group response rates from our BOLD study, a prior, similar study) to support a rational decision about further development of abatacept for SLE.

## 2. STUDY OBJECTIVES

**2.1 Primary Objective:** To compare response rates between Abatacept-Treated and Placebo-Treated Patients with active lupus arthritis in a trial designed with background immune suppressant

withdrawal, limited steroid rescue, and a robust, discriminatory endpoint. Statistical powering is based on this primary objective.

**2.2 Secondary Objectives:** Secondary clinical endpoints will include: SRI 4/5, changes in joint counts, SLEDAI, BILAG, CLASI, PGA, and DIAL measures. We will also Integrate biologic discovery into the clinical trial to support both pre-specified and exploratory biomarker discovery. Data will be generated that might be used to help select more appropriate patient subsets for future trials and to guide optimal dosing strategies. Optimizing patient selection and dosing are important goals for further increasing demonstrable effect size in trials by increasing the response rates in the treatment group.

Optimizing patient selection and dosing are important goals for further increasing effect size in trials. In fact, the two Aims of this project are co-dependent, since each increases the likelihood of interpretable data and could have high impact on increased effect size for an effective product. Also, Aim 2 would be less feasible without the strategy of Aim 1 to decrease the cacophony of background medications, which have clouded interpretation of many treatments for SLE in the past.

## **Ethical Considerations:**

Integration of biologic discovery into clinical trials will generate data that might be used to help select more appropriate patient subsets for future trials and future treatment in clinic and to guide optimal dosing strategies. This is an ethical consideration since it could decrease the numbers of patients inappropriately exposed to a study medication in trials and in practice, and by allowing a better delineation of efficacy in the right population(s) this could also decrease the likelihood of widespread exposure in Phase III trials prior to acquiring sufficient data supporting potential efficacy.

The ethical basis of the current trial design has been debated widely in the lupus community. There is a realistic concern that withdrawal of background therapy will increase the risk of lupus flares and this trial design would be inappropriate for very ill patients such as those with active nephritis. However by decreasing the continued use of background immune suppressants which were obviously not working at the time of entry, by allowing steroid rescue and even restarting of meds as needed during the trial (defining such patients as non-responders) this design could be argued to be far more ethical than trials which legislate continuance of inadequate and potentially toxic background immune suppressant treatments for an entire year, with probable increase in risk for infections. In such protocols, patients who do not improve have only the choice of minimal rescue steroids or to drop out of the study, leading to unnecessary suffering which will not be required in this trial design. Finally, the concern about increasing flare risk should be somewhat alleviated by the results of the MMF, BOLD and Rontalizumab studies (all three of which have been completed using this trial design, and the latter presented at ACR 2012 (39)

### **3.1 Good Clinical Practice**

This study will be conducted in accordance with Good Clinical Practice (GCP), as defined by the International Conference on Harmonization (ICH) and in accordance with the ethical principles underlying European Union Directive 2001/20/EC and the United States Code of Federal Regulations, Title 21, Part 50 (21CFR50).

The study will be conducted in compliance with the protocol. The protocol, any amendments, and the subject informed consent will receive Institutional Review Board/Independent Ethics Committee (IRB/IEC) approval/favorable opinion before initiation of the study.

All potential serious breaches must be reported to Bristol-Myers Squibb (BMS) immediately. A serious breach is a breach of the conditions and principles of GCP in connection with the study or the protocol, which is likely to affect, to a significant degree, the safety or physical or mental integrity of the subjects of the study or the scientific value of the study.

Study personnel involved in conducting this study will be qualified by education, training, and experience to perform their respective tasks. This study will not use the services of study personnel where sanctions have been invoked or where there has been scientific misconduct or fraud (eg, loss of medical licensure; debarment).

### **3.2 Institutional Review Board/Independent Ethics Committee**

Before study initiation, the investigator must have written and dated approval/favorable opinion from the IRB/IEC for the protocol, the informed consent form, subject recruitment materials/process (eg, advertisements), and any other written information to be provided to subjects. The investigator should also provide the IRB/IEC with a copy of the Investigator Brochure or product labeling information to be

provided to subjects, and any updates, as well as descriptions of ancillary pharmacokinetic and pharmaco-dynamics studies.

The investigator should provide the IRB/IEC with reports, updates, and other information (eg, expedited safety reports, amendments, and administrative letters) according to regulatory requirements or institution procedures.

### **3.3 Informed Consent**

Investigators must ensure that subjects or, in those situations where consent cannot be given by subjects, their legally acceptable representative are clearly and fully informed about the purpose, potential risks, and other critical issues regarding clinical studies in which they volunteer to participate. Investigators must:

- 1)** Provide a copy of the consent form and written information about the study in the language in which the subject is most proficient prior to clinical study participation. The language must be non-technical and easily understood.
- 2)** Allow time necessary for subject or subject's legally acceptable representative to inquire about the details of the study.
- 3)** Obtain an informed consent signed and personally dated by the subject or the subject's legally acceptable representative and by the person who conducted the informed consent discussion.
- 4)** Obtain the IRB/IEC's written approval/favorable opinion of the written informed consent form and any other information to be provided to the subjects, prior to the beginning of the study, and after any revisions are completed for new information.
- 5)** If informed consent is initially given by a subject's legally acceptable representative or legal guardian, and the subject subsequently becomes capable of making and communicating their informed consent during the study, then consent must additionally be obtained from the subject.
- 6)** Revise the informed consent whenever new information is available relevant to the subject's consent. The investigator, or a designee should fully inform the subject or the subject's legally acceptable representative or legal guardian, of all pertinent aspects of the study and of any new information relevant to the subject's willingness to continue participation in the study. This communication should be documented.

Minors (subjects under 18) or subjects unable to give informed consent will not be included in this study. The rights, safety, and well-being of the study subjects are the most important considerations and should prevail over interests of science and society.

## 4 INVESTIGATIONAL PLAN

### 4.1 Study Design and Duration

**Planned Study Design:** This will be a randomized, double blind, placebo-controlled trial of patients with active SLE who must have active arthritis (at least BILAG B and at least 3 tender and 3 swollen joints) at the screening visit. Randomization to placebo vs abatacept will be performed on a 1:1 scheme by an unblinded pharmacy technician who will have no contact with study subjects. Patients will give weekly subcutaneous injections of study drug at home except for the first dose which they will give in clinic under the supervision of a nurse/coordinator.

Subjects will be evaluated monthly by an investigator/subinvestigator who are required to have passed LFA testing for Hybrid SLEDAI, BILAG 2004 and CLASI. Additional assays will be PROs (Lupus PRO and SF36) and the DIAL endpoint (endpoints are defined below and case report forms for each endpoint can be found in Appendices). The primary endpoint will be measured at 6 months. This will be a comparison of response rates by the BICLA (BILAG-based Combined Lupus Assessment) which is a scoring system incorporating several measures. Improvement must be documented using the BILAG (British Isles Lupus Assessment Group) index, with no worsening in any organ by BILAG or SLEDAI (SLE Disease Activity Index) and less than 10% worsening in PGA (Physicians Global Assessment) as well as no initiation of off protocol immune suppressants or steroids.

Secondary endpoints will include changes in each of the above mentioned single outcome measures, CLASI, and assessment of patient reported outcomes (secondary endpoints are further described below). Biomarker evaluations with a specific focus on T Cell subset pathways and B Cell pathways will also be explored in a responder analysis.

**Screening procedures:** At the screening visit, patients who are known to have 4 ACR classification criteria (1997 revised) for SLE who present with active arthritis (a minimum of 3 swollen and 3 tender joints) will be invited to undertake screening procedures unless an exclusionary criteria is already known. Screening procedures will begin with the informed consent process during which patients will review the complete informed consent information as approved by the IRB, which will include a full description of the study and the procedures involved, patients' rights and responsibilities, and alternative treatments that are available if the patient does not decide to participate in the study.

Subjects will have a chance to have their questions answered prior to making a decision. Once the informed consent procedures are completed, the following will be completed: medical history, physical examination, review of inclusion and exclusion criteria (some of which will require awaiting blood test results), EKG, PRO measures filled out by the participant (Lupus PRO and SF-36), and clinician measures (SLEDAI, BILAG 2004, CLASI, DIAL, PGA).

To the extent that a history and physical examination was already performed by one of the investigators that day in the course of routine medical care they will not need to be repeated. Screening blood tests will be drawn (maximum 160 cc) including baseline PK and PD samples, and arrangements will be made to contact the patient for the first dosing visit or (if is determined the subject is ineligible) a visit to discuss alternative care. Patients who donate blood at screening for PK and PD and who are later deemed ineligible for the trial will be told, as part of the informed consent process, that these samples may be used for various analyses. Patients retain the right to withdraw

permission for the use of their blood samples at any time. Screening procedures can be performed on the same day the informed consent is signed or any other time up to and including the baseline visit (the screening period) as long as full eligibility is established at the time of randomization.

The study population will include patients between the ages of 18 and 70 who meet a minimum of 4 1997 revised ACR criteria for SLE and who present with a minimum of 3 tender and 3 swollen joints attributable to lupus arthritis. Patients may have other active manifestations of SLE, and, in the opinion of the investigator, they must be sick enough for intention to treat with a biologic and stable enough for this trial design, which includes withdrawal of any background immune suppressants, to be appropriate.

This study will enroll patients until 60 have completed the protocol through at least the six month point. Randomization will be 1:1 to abatacept or placebo. Approximately 30 patients are expected to complete each arm. At each visit history, physical, and blood tests appropriate to complete the outcome measures will be performed, and adverse event reporting and medication updates will be performed.

Subjects may continue to take nonsteroidal anti-inflammatory medications (including *prn* NSAIDS) and up to 20 mg prednisone (or oral steroid equivalent) daily during the study although steroids will be tapered as tolerated. If the patient is taking an immune suppressant (e.g. antimalarials, mycophenolate mofetil, azathioprine, leflunomide, methotrexate, a calcineurin inhibitor or belimumab) at screening, this must be stopped prior to or on the day of the baseline visit. Patients can elect to receive one or more depomedrol injection(s) up to a total of 320 mg total at the time of the screening visit and/or up to and including the Month 2 visit. Daily oral steroids will be tapered as tolerated if and when the patient begins to improve.

Subjects will be encouraged to avoid off protocol medications if possible, but if off protocol medications are given, the patient may, at the discretion of the investigator continue in the protocol as a designated “non-responder”, and continue to be followed at monthly visits until the subjects reaches Month 6. Furthermore, patients may elect to receive open label abatacept as early as Month 3 (three Months after the first Dosing Visit) if their disease activity is not improved at that visit compared to baseline. Such subjects will also be designated as non-responders for the primary endpoint at Month 6. For those patients taking daily oral steroids at screening, they will be encouraged to taper these as tolerated if and when they begin to improve. Patients who withdraw from the protocol for any reason will be encouraged to come for safety follow up visits 2 and 4 months after the last study visit.

The primary endpoint will be determined at six months, but all patients can then choose to receive open label abatacept for an additional six months. Maximal duration of treatment will be 12 months. There will be two follow up visits two and four months after the end of study. However, patients who withdraw after six months will be considered completers of the primary study in the amassing of 60 completers. The criteria for evaluation will be improvement (without worsening) in signs, symptoms and diagnostic results as defined by the BICLA (primary endpoint). Additionally joint counts, the SRI 4/5, hybrid SLEDAI, BILAG 2004, CLASI, DIAL, Lupus PRO and SF-36 will be evaluated.

After receiving the first injection in clinic, patients will administer the study medication at home. Subjects will return to the clinic monthly for six months, and those who continue will be evaluated every 4 weeks for the second six months. There will be two follow up visits at two month intervals after the end of study for each patient. Visits at which maximal blood samples are taken due to PD scheduling are Screening, and Months 3, 6, 9 and 12 (up to 160 cc). At all other visits no more than 80 cc maximally can be drawn.

Please refer to the Time and Events Schedule for a grid of procedures.

## **4.2 Study Population: For entry into the study, the following criteria MUST be met.**

### **4.2.1 Inclusion Criteria**

**1) Signed Written Informed Consent** Before any study procedures are performed, subjects will have the details of the study described to them, and they will be given a written informed consent document to read. Their questions will be answered. Then, if subjects consent to participate in the study, they will indicate that consent by signing and dating the informed consent document in the presence of study personnel.

**2) Target Population:**

Patients with at least 4 1997 revised ACR classification criteria for SLE

Active polyarticular arthritis with a minimum of 3 tender and 3 swollen joints observed at the screening visit and a history consistent with BILAG 2004 “B” arthritis

**3) Age and Reproductive Status**

**Age:** Men and women 18 to 70 years of age.

**Reproductive Status:** *Definition of Women of Child-Bearing Potential (WOCBP).* WOCBP comprises women who have experienced menarche and who have not undergone successful surgical sterilization (hysterectomy, bilateral tubal ligation, or bilateral oophorectomy) or who are not post-menopausal (see definition below)

Post-menopause is defined as:

- i. Women who have had amenorrhea for  $\geq 12$  consecutive months (without another cause)
- ii. Women who have irregular menstrual periods and a documented serum FSH level  $> 35$  mIU/mL.
- iii. Women who are taking hormone replacement therapy (HRT).

The following women are WOCBP:

- iv. Women using the following methods to prevent pregnancy: Oral contraceptives, other hormonal contraceptives (vaginal products, skin patches, or implanted or injectable products), or mechanical products such as intrauterine devices or barrier methods (diaphragm, condoms, spermicides).
- v. Women who are practicing abstinence.
- vi. Women who have a partner who is sterile (eg, due to vasectomy).

WOCBP and sexually active men with WOCBP partners must use contraception throughout the study and for up to 10 weeks after the last dose of study drug. This will be discussed with each subject individually and the plan documented. WOCBP must have a negative urine pregnancy test result (minimum sensitivity 25 IU/L) within 0 to 48 hours before the first dose of study drug and at all subsequent visits. Women must not be breast-feeding.

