Accrual Rate: (Number of subjects expected per month)	We expect to enroll 5 patients/month given entry criteria, recruitment track record, and patient appeal of protocol (in particular the early crossover to open label treatment)
FPFV: LPFV: Follow Up:	
 
• FPFV: October 30 2013
 
• LPFV: December 31 2015
 
• Follow Up: April 31 2016
 

Correlative Studies: (PK/PD, etc.)	Extensive exploratory protocol-specific and ancillary immune pharmacodynamic studies, focusing first on changes in IFN alpha, BLyS and other B Cell pathways. A major focus will also be on T Cell pathways with a focus on T suppressor/TH17 dichotomy after treatment with abatacept. A responder analysis will be performed in order to generate hypotheses useful for selecting appropriate patients for this treatment and optimizing dosing strategies.
Inclusion Criteria:	
 
1) Signed Written Informed Consent
 
2) 4 1997 revised ACR Classification Criteria for SLE
 
3) Active polyarticular arthritis meeting at minimum BILAG 2004 B definition with a minimum of 3 tender and 3 swollen joints observed at the screening visit
 
4) Men and women 18 to 70 years of age.
 
5) Women of childbearing potential and men with partners of childbearing potential must use an acceptable method of birth control throughout the study
 
6) Women of childbearing potential must have a negative urine pregnancy test at screening and Study Day 1 (baseline visit) and may not be breast feeding
 

Exclusion Criteria:	
 
1) Current severe disease (e.g. acute nephritis appropriate for induction therapy, CNS lupus (excepting chorea, cranial neuropathy, and resolving optic neuritis) or any lupus condition requiring cyclophosphamide, biologic therapy, or IV bolus steroids of <math>\geq</math> 500 mg.
 
2) Subjects who are incapable of understanding or
 

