### 1.3.2 Human Pharmacokinetics of Abatacept

**Support for SC dosing route:** Single subcutaneous (SC) dose study of abatacept (50 to 150 mg) where escalating, single, fixed doses were administered demonstrated approximately dose proportional PK in healthy adult subjects based on the geometric means of Cmax and AUC(INF) values (30). The median time to occurrence of Cmax (Tmax) following SC administration ranged between 48-168 hours. Mean T1/2 values in healthy subjects ranged 11.2 to 14.7 days, which was comparable with the T1/2 values obtained with abatacept administered IV to subjects with RA (13 to 14 days) (30). The fact that T1/2 values following SC dosing were comparable to T1/2 values obtained after IV dosing suggests that the SC administration did not alter elimination of abatacept.

Although subcutaneous administration has not been studied previously in SLE, key information about subcutaneous dosing of abatacept in a comparable population can be inferred through data from the IM101063 trial in rheumatoid arthritis. A double-blind, randomized, placebo-controlled, parallel-group, multiple-dose study (IM101063) assessed the steady-state trough serum concentrations of abatacept following SC administration in subjects with RA (31). Subjects were randomized to receive either abatacept or placebo in 1 of 5 parallel groups based on body weight obtained at the screening visit (Table 1.3.2A). The SC dose regimens were selected to target trough levels between 10-30 µg/mL, which was associated with efficacy with the IV formulation.

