### **7.5 Pregnancy**

If, following initiation of the investigational product, it is subsequently discovered that a study subject is pregnant or may have been pregnant at the time of investigational product exposure, including during at least 6 half lives after product administration, the investigational product will be permanently discontinued in an appropriate manner (eg, dose tapering if necessary for subject safety).

Protocol-required procedures for study discontinuation and follow-up must be performed on the subject unless contraindicated by pregnancy (eg, x-ray studies). Other appropriate pregnancy follow-up procedures should be considered if indicated.

The investigator must immediately notify the BMS (or designee) Medical Monitor of this event and complete and forward a Pregnancy Surveillance Form to BMS (or designee) within 24 hours and in accordance with SAE reporting procedures described in Section 7.2.1

Follow-up information regarding the course of the pregnancy, including perinatal and neonatal outcome and, where applicable, offspring information must be reported on the Pregnancy Surveillance Form.

Any pregnancy that occurs in a female partner of a male study participant will be reported to BMS. Information on this pregnancy will be collected on a Pregnancy Surveillance Form.

**7.6 Potential Drug-Induced Liver Injury (DILI):** Wherever possible, timely confirmation of initial liver-related laboratory abnormalities should occur prior to the reporting of a potential DILI event. All occurrences of potential DILIs, meeting the defined criteria, must be reported as SAEs (see Section 7.2.1 for reporting details).

Potential drug induced liver injury is defined as

1. AT (ALT or AST) elevation > 3 times upper limit of normal (ULN)  
AND
2. Total bilirubin > 2 times ULN, without initial findings of cholestasis (elevated serum alkaline phosphatase),  
AND
3. No other immediately apparent and/or possible causes of AT elevation and hyperbilirubinemia, including, but not limited to, viral hepatitis, pre-existing chronic or acute liver disease, or the administration of other drug(s) known to be hepatotoxic.

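### The 10-week limit on contraception after the last dose can end before the protocol's own six-half-life exposure window for a pregnant participant

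*Combined protocol and SAP*

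**What the plan says.** Section 4.2.1, under Age and Reproductive Status, says that women of childbearing potential and sexually active men with such partners "must use contraception throughout the study and for up to 10 weeks after the last dose of study drug". It adds that the plan is discussed with each subject and documented. The corresponding synopsis criterion (Inclusion Criteria, item 5) says only that they "must use an acceptable method of birth control throughout the study" and gives no period after the last dose.

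Section 7.5 covers a study subject who is found to be pregnant or who "may have been pregnant at the time of investigational product exposure, including during at least 6 half lives after product administration". It does not convert the half-lives into days.

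Section 1.3.2 holds the only half-lives in the document. For subcutaneous dosing, mean "values in healthy subjects ranged 11.2 to 14.7 days". It calls these comparable with "values obtained with abatacept administered IV to subjects with RA (13 to 14 days", and infers that the subcutaneous route did not alter elimination.

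On follow-up, Section 4.1 says: "There will be two follow up visits two and four months after the end of study". The Study Design row of the synopsis, Section 4.2.3 and Section 5.3 instead treat those visits as part of the study.

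**The concern.** The two clauses concern the same interval after the last dose, and they are bounded in opposite directions: contraception by a maximum, exposure by a minimum. If six half-lives is longer than 10 weeks, a female participant could follow the 10-week clause exactly, stop, conceive a week or two later, and have a pregnancy that Section 7.5 still counts as exposed.

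The stake is participant safety and clear instructions to the site. Section 1.3.3 itself describes pregnancy experience with abatacept as limited. The site also has no number of days with which to apply the exposure window. Efficacy, power and type I error are not involved.

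**Working it through.** There is no figure of the plan to reproduce. The protocol gives no derivation for the 10 weeks and never states six half-lives in days. Ten weeks equals 5 × 14 days, but nothing in the text says that this is its basis.

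**Inputs**

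- Limit after the last dose (Section 4.2.1): 10 × 7 = 70 days at most.
- Exposure window (Section 7.5): 6 × T½ at least.
- T½, rheumatoid arthritis, intravenous (Section 1.3.2): 13 to 14 days.
- T½, healthy subjects, subcutaneous, range of means (Section 1.3.2): 11.2 to 14.7 days.
- T½ in lupus: not given, so the full range is shown.

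**Formula:** difference = 6 × T½ − 70. A positive value means that the limit ends first.

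| T½ (days) | Source | 6 × T½ (days) | Difference (days) | 70 days in half-lives |
|---|---|---|---|---|
| 11.2 | healthy, SC, low | 67.2 | −2.8 | 6.25 |
| 13 | RA, IV, low | 78 | +8 | 5.38 |
| 14 | RA, IV, high | 84 | +14 | 5.00 |
| 14.7 | healthy, SC, high | 88.2 | +18.2 | 4.76 |

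**Break-even:** 70 / 6 = 11.67 days. Only the bottom of the subcutaneous range lies below it.

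**Does the requirement to use contraception during the study close the difference?** That depends on where the study ends.

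- *Follow-up inside the study.* The synopsis lists the 2- and 4-month visits in its design row, Section 4.2.3 makes them part of completing the protocol, and Section 5.3 places them at Months 14 and 16. Four months is about 4 × 30 = 120 days, beyond the longest window of 88.2 days. A participant who stays to the last visit then has no shortfall. The 10-week clause matters only for someone who leaves sooner.
- *Follow-up outside the study.* Section 4.1 dates both visits from the end of study. The 10-week clause is then the only limit after treatment, and the table applies to every female participant to whom the contraception requirement applies.

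Early leavers are uncertain on either reading. Section 4.1 only encourages those who withdraw to attend the two visits, and Section 4.2.3 exempts those who withdraw consent.

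The Time and Events Schedule marks pregnancy tests at the follow-up visits, at about 60 and 120 days. Days 70 to 88 fall between them, and a test detects a pregnancy without preventing it.

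**The case against.** The strongest reply is that contraception is required for the whole study as well as for the post-dose period. If the study includes follow-up, a participant who stays is covered for about four months, and the 10-week clause is a sensible backstop for those who leave. This stands as a possible reading. It is why the point is an inconsistency and not a demonstrated shortfall for every participant. Section 4.1 still contradicts it, and the backstop itself can end inside the exposure window.

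A second reply is that the clauses serve different purposes: one governs conduct, the other pregnancy action and surveillance. Nothing in the protocol requires them to be equal, and a longer surveillance window is not in itself an error. That is fair, but the protocol does not say that the difference is intended.

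Third, the half-lives are borrowed. None comes from lupus, and the 78 to 84 days rests on intravenous dosing in another disease. The subcutaneous values give 67 to 88 days, which straddle 70. This stands as a limit on the size. Section 1.3.2 does treat the two sets as comparable.

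A reader might also infer three things that the documents do not support:

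- *That the same window applies to partners of male participants.* Section 7.5 ties the six half-lives to a study subject. Partner pregnancies have a separate sentence with no such window.
- *That the gap creates an additional 24-hour reporting duty.* Section 7.2.1 already requires every pregnancy to be reported within 24 hours, whatever the time since the last dose.
- *That stopping at any time before 10 weeks is plainly compliant.* The wording sets no minimum, but it stands beside a mandatory verb and an individually documented plan. It is unclear; it is not a clear permission.

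**Conclusion.** The inconsistency is real but modest. For a female participant, a limit of at most 70 days ends before an exposure window of at least six half-lives whenever the half-life exceeds about 11.7 days. The difference is 8 to 14 days at the rheumatoid arthritis values and runs from none (2.8 days to spare) to 18.2 days across the subcutaneous values.

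This rests on two assumptions: that elimination in lupus resembles the populations in Section 1.3.2, and that the 10-week clause is the operative limit, either because follow-up lies outside the study or because the participant leaves early. No calculation in the protocol is wrong. A reader might conclude that the contraception period must be lengthened. The documents do not show which passage is the right one, so the finding is only that they must be reconciled.

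**What to change.** Reconcile synopsis Inclusion Criteria item 5, Section 4.2.1 and Section 7.5, and carry the result into the consent form:

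1. State whether the study, for the purpose of the contraception requirement, includes the 2- and 4-month follow-up visits, and align Section 4.1 with the synopsis design row and Sections 4.2.3 and 5.3.
2. Give the Section 7.5 exposure window in days, from one stated half-life with its source.
3. Replace the open-ended limit with a definite period that is consistent with that window, repeat it in the synopsis, and say how it applies to participants who stop early.

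The sponsor decides the length. The cost is wording in the protocol and consent form, with no effect on sample size or analysis. The small downside is that the contraception period may change for some participants.
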